### **4.3 Radiation-Specific Safety Guidelines**

The radiation fractionation scheme proposed in this study (33 Gy in 5 fractions) was evaluated in a prospective multi-institutional phase II study in which patients with locally advanced pancreatic cancer received gemcitabine followed by SBRT. The rate of grade 3 or higher acute GI toxicity was 2% and the rate of grade 3 or higher late GI toxicity was 8%. Based upon this study and other published studies evaluating multi-fraction SBRT for pancreatic cancer, a rate of grade 3 GI toxicity of 20% or higher would be unexpected. An interim safety analysis will be performed by the PI after 5 patients complete 3 months of follow-up after SBRT. Study accrual will continue during this time period. If the rate of grade 3 GI toxicity that is probably related to SBRT exceeds 20%, then accrual will be held and the protocol and consent will be revised.

Refer to section 7 for recommendations for the management of toxicities related to SBRT.

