## 12. STATISTICAL METHODS

The primary endpoint of this phase II study is the R0 resection rate after neoadjuvant mFOLFIRINOX and SBRT in patients with BRPC.

In the largest reported series of patients with BRPC, 125 patients received pre-operative therapy consisting of 2 to 4 months of gemcitabine-based chemotherapy followed by fractionated chemoradiation. 41% of patients underwent a subsequent resection, and R0 resections were achieved in 94% of these patients, for an overall R0 resection rate of 39% for all patients initiating pre-operative therapy. Superior outcomes have been demonstrated with FOLFIRINOX compared to gemcitabine chemotherapy, and a local control benefit has been suggested with SBRT compared to fractionated chemoradiation. Thus, we propose an increase in the R0 resection rate from 40% in historical controls treated with standard gemcitabine-based chemotherapy and fractionated radiation prior to surgery to 65% with pre-operative FOLFIRINOX and SBRT.

A total of 28 patients will be enrolled in a Simon two-stage design with a provision for early stopping for lack of efficacy. The primary endpoint is the rate of achieving R0 resections. Patients needing to drop out of this study prior to surgery, for disease progression or treatment related toxicity, will be considered as failing to achieve the R0 resection rate. The null hypothesis is this rate is 40% based on both reported historical rates as well as our experience at Yale-New Haven Hospital. Under the alternative hypothesis, we will judge pre-operative modified FOLFIRINOX followed by SBRT effective if the R0 resection rate is 65% or higher. The optimal Simon two-stage design will terminate early if 5 or fewer of the first 13 patients fail to achieve an R0 resection. Otherwise we continue and enroll the remaining 15 patients for a total of 28. If 15 or more out of the full 28 achieve R0 resection then we reject the null hypothesis. This design has 90% power and significance level 0.1. The probability of stopping early under the null hypothesis is 57%.

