## **15. YALE SAFETY REPORTING AND MONITORING (DSMP)**

The principal investigator at the Yale Cancer Center will monitor the clinical trial for safety. The principal investigator will assess all expedited adverse events and will periodically review all adverse events observed on the trial. Yale Cancer Center standard operating procedures (SOPs) for assessment and reporting of adverse events are followed which are in compliance with FDA 21 Code of Federal Regulations Part 312.32 and 312.33.

The clinical trial data consisting of all required observations, AEs, and laboratory data will be entered into a computerized database (OnCore) in a timely manner. The accuracy and completeness of the database, timely submission of SAEs and compliance with the protocol, is assured by periodic auditing conducted by the Yale Cancer Center Office of Protocol Review and Monitoring, which reports to the

Yale Data and Safety Monitoring Committee (DSMC). Safety data will be submitted to DSMC at least once yearly or more often as required by the DSMC. On a regular interval basis, status reports of all laboratory parameters, AEs and SAEs are reviewed by the PI to view composite data across subjects. Regular meetings are held to discuss ongoing patient treatment and adverse events.

The Yale DSMC will perform an interim safety analysis after enrollment of 10 patients to determine whether there are any safety issues and to assess whether it is safe to continue enrollment. Enrollment will be suspended until approval is granted from the DSMC to proceed completion of enrollment.

Possible actions taken by the PI or the Yale DSMC if a new unexpected toxicity is identified from the above safety review, or if the periodic review of all adverse events and laboratory data indicates a pattern of incidence or severity of toxicity that raises a safety concern, can be to:

- Revise consent form
- Amend the protocol
- Suspend the protocol

All AEs found to be expected or non-serious, will be included in the Annual Report.

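### The only numeric SBRT toxicity rule is scheduled once, at 5 patients; it needs 2 of 5 to act and would hold accrual with only 26% probability at a true rate of 20%

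*Combined protocol and SAP*

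**What the plan says.** Section 4.3 sets the timing: "An interim safety analysis will be performed by the PI after 5 patients complete 3 months of follow-up after SBRT". On accrual it adds: "Study accrual will continue during this time period". The action limit is: "If the rate of grade 3 GI toxicity that is probably related to SBRT exceeds 20%, then accrual will be held", after which the protocol and consent are to be revised. Just before this, the section summarises the literature and concludes that "a rate of grade 3 GI toxicity of 20% or higher would be unexpected". The reference rates it gives from the earlier phase II SBRT study are 2% for acute and 8% for late GI toxicity of grade 3 or higher.

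No later application of this limit is scheduled, and no operating characteristics are given for it. Section 12 sets the size of the trial: "A total of 28 patients will be enrolled in a Simon two-stage design".

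Section 15 provides a further review: "The Yale DSMC will perform an interim safety analysis after enrollment of 10 patients". Enrollment is suspended until the committee approves. Section 15 also requires safety data to go to the DSMC at least yearly, has the PI review pooled adverse events, and lets the PI or the DSMC suspend or amend the protocol. Section 14.1 requires expedited reporting to the institutional committee when anticipated events are more frequent than expected. Section 11 lets the PI terminate the study on safety grounds. None of these gives a numeric limit for GI toxicity.

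**The concern.** The possible observed rates in 5 patients are 0, 20%, 40% and so on. One event is exactly 20%. That falls in the range the protocol calls unexpected, yet it does not go above 20%, so nothing follows. Action needs 2 events, an observed 40%. The two wordings differ only at exactly 20%, but with 5 patients that decides whether one event counts.

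Two things are at stake. A single look at 5 patients has a low chance of acting at the rates the protocol itself treats as out of line. And once it has passed, no numeric rule is scheduled for the other 23 of the 28 patients.

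The 3-month window adds to this. Section 2.2.4 defines late toxicity as more than 3 months after radiation, so the look mainly covers the acute period, although the larger reference rate (8%) is for late events.

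**Working it through.** **Inputs.** From Section 4.3: n = 5, a hold if the observed rate is strictly above 20%, reference rates 2% and 8%. The 10% scenario adds the acute and late rates and assumes they do not overlap. The protocol states no error rate for this rule, so there is no figure to reproduce.

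**Single look.** A hold needs X ≥ 2 of 5, so P(hold) = 1 − (1−p)^5 − 5p(1−p)^4.

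- p = 0.08: 1 − 0.6591 − 0.2866 = 0.054
- p = 0.10: 1 − 0.5905 − 0.3281 = 0.081
- p = 0.20: 1 − 0.3277 − 0.4096 = 0.263
- p = 0.30: 1 − 0.1681 − 0.3602 = 0.472
- p = 0.40: 1 − 0.0778 − 0.2592 = 0.663

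A true 20% rate therefore passes the look about 74% of the time, and a true 40% rate about one time in three.

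**Re-applying the same limit.** The smallest counts strictly above 20% are 2 of 5, 3 of 10, 4 of 15 and 5 of 20. The cumulative chance of a hold follows by exact recursion over the paths not yet held. For example, by the look at 10 with p = 0.20, where Y is the count in the second five patients:

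P(hold at 5) + P(X=0)·P(Y≥3) + P(X=1)·P(Y≥2) = 0.2627 + 0.3277×0.0579 + 0.4096×0.2627 = 0.389.

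| Looks at | 8% | 10% | 20% | 30% | 40% |
|---|---|---|---|---|---|
| 5 only | 5.4% | 8.1% | 26.3% | 47.2% | 66.3% |
| 5, 10 | 7.3% | 11.3% | 38.9% | 66.9% | 86.0% |
| 5, 10, 15 | 8.1% | 12.9% | 46.7% | 77.5% | 93.5% |
| 5, 10, 15, 20 | 8.5% | 13.8% | 52.1% | 84.0% | 96.8% |

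**The other wording.** If 20% itself triggered a hold (1 of 5, 2 of 10, 3 of 15, 4 of 20), the chance at a true 20% would be 67% at the first look. At a true 8% it would be 34% at the first look and 39% over four looks.

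**What the DSMC would see at 10 enrolled.** Time from enrollment to 3 months after SBRT:

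- 8 two-week cycles: 16 weeks (Section 6.1)
- gap to SBRT: 0 to 4 weeks (Section 3.1)
- SBRT: 2 to 3 weeks (Section 6.2.4)
- follow-up: 13 weeks
- total: 31 to 36 weeks

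Assume uniform accrual and that every patient reaches SBRT.

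- At 6 a year (Section 3.4), spacing is 52/6 = 8.67 weeks and the 10th patient enrolls at week 78. Patients enrolled by week 42 to 47 are evaluable, which gives 5 to 6.
- At 14 a year (28 in two years, Section 12), spacing is 3.71 weeks and the 10th enrolls at week 33.4. Patients enrolled by week 2.4 at the latest are evaluable, which gives 0 to 1.

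**Would later looks fall within accrual?** Under the same assumptions:

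- At 14 a year, the 28th patient enrolls at about week 100. The 15-patient look falls at 14×3.71 + 31 to 36 = week 83 to 88, and the 20-patient look at 19×3.71 + 31 to 36 = week 102 to 107.
- At 6 a year, accrual ends at week 234 and the 20-patient look falls at week 196 to 201. If 20% dropped out before SBRT (an assumption), the 20th SBRT patient would be the 25th enrolled, and the look would fall at 24×8.67 + 31 to 36 = week 239 to 244.

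**The case against.** The look can fairly be read as an early check for a gross excess on a fractionation already studied: its chance of a hold is 81% at a true 50%. The protocol claims no power for it, and requiring 2 events avoids holding accrual on a single one. The two 20% phrases also do different jobs, one summarising the literature and the other setting the action limit. All of this is reasonable, but it does not explain why the limit is not scheduled again as data accumulate.

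A reader might infer that the rule cannot detect a 20% rate. That goes too far: it does so with probability 26%.

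A reader might also infer that later patients have no protection. The documents do not support that. The DSMC review at 10 enrolled suspends enrollment, which is stronger than the PI look, during which accrual continues. There are also at least yearly DSMC submissions, PI review, expedited reporting of excess frequency and the PI's right to terminate. The gap is the absence of a scheduled numeric GI limit, not of oversight. The conditional sentence in Section 4.3 could even be read as a standing rule, though no later look is named.

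Nor does it follow that the DSMC will see no SBRT data. At 6 a year, the rate consistent with 28 patients in 56 months, it would have 5 to 6 evaluable patients. The 0 to 1 figure needs the conflicting two-year statement in Section 12.

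Finally, the gain from a 20-patient look should not be taken for granted, since accrual may be over by then.

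**Conclusion.** The point holds as an inexpensive safety improvement. The only numeric SBRT limit is scheduled once, acts at 2 of 5, and holds accrual with probability 26%, 47% and 66% at true rates of 20%, 30% and 40%. No later review carries a GI number, and the DSMC review is tied to enrollment rather than SBRT exposure.

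The binomial figures assume independent patients with a common probability of a qualifying event by the time of each look. The evaluable counts assume uniform accrual and no loss before SBRT; any loss lowers them. They also depend on which of the two conflicting accrual statements is right. The safest estimate of the benefit is the one for looks at 5, 10 and 15. The figures that include a look at 20 apply only if accrual is still open then.

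**What to change.** Keep the sponsor's existing action limit and make four changes.

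1. In Section 4.3, state the limit as a count of patients, with SBRT-treated patients who have 3 months of follow-up as the denominator. Under the present limit this is 2 of 5, 3 of 10, 4 of 15 and 5 of 20.
2. Re-apply it cumulatively while accrual is open, for example at 10 and 15 evaluable patients, and at 20 if accrual has not closed. Earlier patients' late events then enter the later counts.
3. In Section 15, give the DSMC the number of SBRT-evaluable patients and their GI events at the 10-patient review.
4. Reconcile the statement that 20% or more is unexpected with the limit that acts only above 20%. The choice is the sponsor's and no threshold is proposed here. Acting at 20% itself would carry the false-hold chances shown above (34% at the first look and 39% over four looks, at a true 8%).

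The cost is two or three short tabulations of data already collected, since grade 3 or greater GI toxicity is a secondary outcome (Section 3.3.2). Under the present limit, the chance of an unnecessary hold rises from 5.4% to about 8.1–8.5% at a true 8%, and from 8.1% to 12.9–13.8% at a true 10%.

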## 5. ELIGIBILITY CRITERIA

### 5.1 Disease Characteristics

- 5.1.1 Histologically confirmed pancreatic adenocarcinoma
- 5.1.2 Borderline resectable pancreatic adenocarcinoma, determined centrally by review of a diagnostic CT scan and/or MRI scan with contrast by a dedicated surgical oncologist and radiologist, or as determined by EUS, and defined according to one of the following four NCCN consensus guidelines:
  - Tumors of the pancreatic head or uncinate process with:
    - Solid tumor contact with the common hepatic artery (CHA) without extension to the celiac axis (CA) or hepatic artery bifurcation allowing for safe and complete resection and reconstruction, or
    - Solid tumor contact with the superior mesenteric artery (SMA) of ≤180 degrees, or
    - Presence of variant arterial anatomy such that the degree of tumor contact affects surgical planning
  - Tumors of the pancreatic body or tail with:
    - Solid tumor contact with the CA of ≤180 degrees, or
    - Solid tumor contact with the CA of >180 degrees without involvement of the aorta and with intact and uninvolved gastroduodenal artery
  - Solid tumor contact with the superior mesenteric vein (SMV) or portal vein (PV) of >180 degrees, or contact of ≤180 degrees with contour irregularity of the vein or thrombosis of the vein but with suitable vessel proximal and distal to the site of involvement allowing for safe and complete resection and vein reconstruction
  - Solid tumor contact with the inferior vena cava (IVC)
- 5.1.3 No evidence of extrapancreatic disease on diagnostic imaging (CT, MRI, or PET scan), or laparoscopy, including nodal involvement beyond the peripancreatic tissues and/or distant metastases
- 5.1.4 No evidence of invasion into the duodenum or stomach, as determined by EGD/EUS

### 5.2 Prior Therapy

- 5.2.1 No prior treatment (chemotherapy, biological therapy, or radiotherapy) for pancreatic cancer
- 5.2.2 No prior treatment with oxaliplatin, irinotecan, fluorouracil or capecitabine
- 5.2.3 Patients who received chemotherapy >5 years ago for malignancies other than pancreatic cancer are eligible
- 5.2.4 No major surgery within 4 weeks of study entry
- 5.2.5 No other concurrent anticancer therapy

### 5.3 Patient Characteristics

- 5.3.1** ECOG Performance Status of 0-1
- 5.3.2** Age  $\geq 18$
- 5.3.3** No other malignancy within past five years (exceptions include basal cell carcinoma of the skin, cervical carcinoma in situ, and nonmetastatic prostate cancer)
- 5.3.4** No evidence of second malignancy at the time of study entry
- 5.3.5** No interstitial pneumonia or extensive and symptomatic interstitial fibrosis of the lung
- 5.3.6** No  $\geq$  grade 2 sensory peripheral neuropathy
- 5.3.7** No uncontrolled seizure disorder, active neurological disease, or known CNS disease
- 5.3.8** No significant cardiac disease, including the following: unstable angina, New York Heart Association class II-IV congestive heart failure, myocardial infarction within six months prior to study enrollment
- 5.3.9** Not pregnant and not nursing
- 5.3.10** No other medical condition or reason that, in the opinion of the investigator, would preclude study participation
- 5.3.11** Laboratory parameters as follows:
  - Absolute neutrophil count  $\geq 1,500/\mu\text{L}$ ,
  - Platelet count  $\geq 75,000/\mu\text{L}$ ,
  - Hemoglobin  $\geq 9 \text{ g/dL}$ ,
  - Creatinine  $< 1.5 \times \text{ULN}$  or estimated GFR  $> 30 \text{ ml/min}$ ,
  - Bilirubin  $\leq 1.5 \times \text{ULN}$ ,
  - AST and ALT  $\leq 3 \times \text{ULN}$ ,
  - Negative pregnancy test in women of childbearing potential
- 5.3.12** Able to be treated with SBRT only at the Smilow New Haven campus
- 5.3.13** Able to have fiducials placed in the pancreas

## 6. TREATMENT PLAN

This is a non-randomized phase II study. Treatment will be administered on an outpatient basis under medical supervision. Protocol treatment will begin within 14 days of registration.

### 6.1 Neoadjuvant mFOLFIRINOX

Patients will receive eight cycles of neoadjuvant mFOLFIRINOX – one cycle every two weeks (+/- 3 days). One cycle is defined as 14 days, and treatment will be initiated on day one of a two week cycle. The drugs will be dosed and administered as follows:

- Oxaliplatin  $85 \text{ mg/m}^2$  IV infused over two hours, followed by
- Leucovorin  $400 \text{ mg/m}^2$  IV (or levoleucovorin  $200 \text{ mg/m}^2$  IV) over two hours
- Irinotecan  $135 \text{ mg/m}^2$  IV over 90 minutes (concurrent with leucovorin during the last 90 min of the leucovorin infusion)
- 5-FU  $300\text{mg/m}^2$  IV bolus, then  $2400 \text{ mg/m}^2$  continuous IV infusion over 46 hours

All patients will receive supportive care as follows:

- Pegfilgrastim (NeulastaTM) on day 3, 4, or 5.

- Anti-emetics including palonosetron or ondansetron, aprepitant, and dexamethasone, according to standard institutional protocols.
- Atropine is administered per standard guidelines for cholinergic symptoms during irinotecan infusion on day 1.
- Loperamide is administered per standard guidelines for chemotherapy-induced diarrhea.
- Patients will be counseled regarding potential side effects and their management.

Re-staging pancreas protocol CT scans will be performed after 3 and 7 cycles of mFOLFIRINOX. MRI can be substituted for patients unable to undergo a CT scan. A PET scan is optional if necessary for re-staging.

## **6.2 Neoadjuvant SBRT**

Patients without evidence of distant progression will receive SBRT directed at the primary tumor. An 8th cycle of mFOLFIRINOX will be administered during planning for SBRT. All patients will be maintained on proton pump inhibitors beginning with the first SBRT treatment and continuing for at least 6 months after completion of SBRT, or until surgery if undergoing resection.

### **6.2.1 Fiducials**

Patients will undergo an EUS for placement of 1-5 gold fiducials to guide radiation delivery. The fiducials will be placed directly in the tumor or surrounding normal pancreas under endoscopic guidance. The fiducials will be used as a surrogate for tumor position on the day of each treatment. A core biopsy and elastography measurements will be obtained at the time of fiducial placement. If a core biopsy is attempted but not successful, or elastography is not feasible, patients can continue on study.

### **6.2.2 Simulation**

CT simulation for radiation planning will be performed after the placement of fiducials. Patients will be NPO 3 hours prior to the scan, with the exception of oral contrast 30 minutes prior to the scan. Patients will be positioned supine in a custom vac-loc immobilization device. A dual phase (arterial and venous) IV contrast scan with 1.25mm slices will be obtained for target delineation. If the patient cannot tolerate IV contrast, the scan will be obtained without contrast and merged to diagnostic imaging (MRI, PET, and/or prior CT with contrast) for target delineation. A 4D-CT scan (with 2.5mm slice thickness) will then be obtained to characterize tumor motion with respiration. Abdominal compression will be applied for respiratory motion management, with the goal of decreasing motion of the fiducials to 5mm or less. The IV contrast and 4D scans will include from the carina to the iliac crests. Patients must begin SBRT within 3 weeks of the simulation scan.

### **6.2.3 Treatment Planning**

The planning arterial and venous phase IV contrast scans will be fused to the 4D scan for target delineation. Diagnostic imaging including MRI or PET scans can also be fused to the treatment planning scans if deemed helpful for contouring the tumor. The tumor volume (GTV) will include the primary tumor and any involved peripancreatic nodes. An internal target volume (ITV) will be generated using the 4D scan to account for motion of the GTV with respiration. The planning target volume (PTV) will consist of a 2-3mm volumetric expansion of the ITV, except if the expansion includes the duodenum or

stomach, in which case a non-uniform expansion margin is acceptable to limit dose to these surrounding normal tissues. Treatment planning will be carried out on the average of the 4D scan, using IMRT (including volumetric-arc therapy [VMAT]), or 3D conformal techniques.

The prescription dose will be 33 Gy in 5 fractions of 6.6 Gy over the course of 2 weeks.

The following normal tissue constraints will serve as guidelines for treatment planning, as per prior studies evaluating the dosimetric determinants of duodenal toxicity with SBRT and the dose constraints established in prior trials. In the circumstance where the following constraints cannot be met, exceptions will be recorded and treatment can proceed with PI approval.

- Proximal Duodenum (the entire duodenum on the same axial plane as the PTV, and the duodenum 1 cm above and 1 cm below the PTV):
  - <1cc to 33 Gy
  - <9cc to 15 Gy
  - <3cc to 20 Gy
  - If <9cc to 15 Gy and/or <3cc to 20 Gy can not be met, <5cc of small bowel including duodenum to 18 Gy is acceptable
- Small Bowel:
  - <1cc to 33 Gy
  - <9cc to 15 Gy
  - <3cc to 20 Gy
  - If <9cc to 15 Gy and/or <3cc to 20 Gy can not be met, <5cc of small bowel including duodenum to 18 Gy is acceptable
- Stomach:
  - <1cc to 33 Gy
  - <9cc to 15 Gy
  - <3cc to 20 Gy
  - If <9cc to 15 Gy and/or <3cc to 20 Gy can not be met, <5cc of stomach to 28 Gy is acceptable
- Liver:
  - 50% <12 Gy
- Combined Kidneys:
  - 75% <12 Gy
- Spinal Cord:
  - <1cc to 8 Gy
  - 30 Gy point max

The following treatment planning goals will be achieved:

- No more than 1cc of the PTV can receive >130% of the prescription dose
- Greater than 90% of the PTV should receive 100% of the prescription dose
- If the above normal tissue constraints can not be met, then 100% of the ITV will receive at least 25 Gy

#### **6.2.4 Treatment Delivery**

Linac-based SBRT will be delivered to a total dose of 33 Gy in 5 fractions over the course of 2 weeks, or maximum of 3 weeks (21 days). The fiducials will be contoured to aid in target localization. A cone beam CT (CBCT) will be obtained in the treatment position on the Linac prior to each treatment. The fiducials will be visualized on the day of treatment CBCT, and the patient position will be adjusted to align the fiducials to match that of the planning CT scan.

